In this double-blind research study, 66 participants will be randomized to receive real or sham tDCS prior to receiving an established interactive upper limb (shoulder/elbow and wrist) robotic training regimen. During the lead-in period, each subject will attend 3 weekly visits to complete TMS screening and have outcome measures (see below) assessed. Following the lead-in period, each subject will attend 36 90-minute sessions (3 visits/week) over a 12-week period (or up to 14-weeks to allow for missed appointments) comprising the training period. These visits will include further TMS screening and outcome measures, TMS, tDCS and robot training. Subjects will undergo further outcomes measures upon discharge and during a final 6-month follow-up visit. All study procedures will be administered and supervised by a therapist. All visits will be conducted in either the robot and TMS suites at the Feinstein Institute for Medical Research or at the Burke Medical Research Institute (Fig. 1). Participants will additionally undergo five blood draws longitudinally during the study to determine if cytokine levels change over the course of rehabilitation intervention, and if those changes are correlated with improved functional outcomes and treatment group (sham vs. real tDCS).

Lead-in Period

- Week 1, Visit 1 (approximately 30 minutes)
 - TMS screening questionnaire
 - Outcome measures
- Week 2 & 3, Visit 2 & 3 (approximately 60 minutes each)
 - Outcome measures
 - One time 10cc DNA sample and 2 separate 4cc baseline blood draws (2 total draws)

Training Period

- Week 4-15, Visits 4-39 (approximately 90 minutes)
 - TDCS risk questionnaire (visit 4 only)
 - TMS
 - tDCS
 - Robotic training
 - 4cc blood draw at midpoint, session 18 (1 total)
- Weeks 16 Visit 40 (approximately 2.5 hours)
 - tDCS

[figure not shown]

Fig 1: Diagram of study design showing the relationship between the robotic training program with or without tDCS and the evaluation schedule

- Robotic training
- Outcomes measures
- 4cc discharge blood draw (1 total)

Final Visit

- Week 40, Visit 41 (approximately 60 minutes)
 - Outcome measures
 - 4cc follow up blood draw (1 total)

Clinical Outcome Measures

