All outcome measures will be recorded three times prior to the training period separated by one week to ensure reliability and stability of measures, then again following the 12-week training program, and six months later. In general, study visits will take place at the institution of recruitment (e.g. subjects recruited through Feinstein will be treated at Feinstein). However, occasionally TMS and clinical assessments may take place at the other institute. Individual patient assessments will always be performed by the same evaluator to ensure internal consistency.

Fugl-Meyer (Primary): The Fugl-Meyer scale is a valid and reliable evaluation instrument used for measuring performance-based impairment in stroke patients (54, 55).

Medical Research Council motor power score (MRC): The MCR is a valid and reliable score that measures strength in isolated muscle groups of the involved shoulder and elbow on an ordinal scale (scale range: 0, no muscle contraction; 5, normal strength) .

Wolf Motor Function: The Wolf Motor Function Test is a valid and reliable assessment of upper extremity function by asking the patient to complete 15 motor-based tasks and two strength-based tasks (56).

Barthel Index (BI): The BI is a valid and reliable index of independence widely used in scoring improvement in the rehabilitation of stroke population (57). The BI consists of 10 items assigned various weightings: 15 points for the subcategories of walking and transfers; 10 points for the subcategories of feeding, bowel, bladder, toileting, dressing and stairs; 5 points for the subcategories of bathing and grooming. The BI is a cumulative score achieved by summing the score for all sections. The BI scores are recorded in multiples of 5, ranging from 0 (completely dependent) to 100 (independent in basic activities of daily living).

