Patients will sit in a comfortable chair and a plastic band will encircle the skull. An electrode – a flat 6cm X 6cm plate – will be ensheathed in a disposable cotton sponge and held in place by the band. The electrode (cathode) covered by the pad will be placed above the eye and on the forehead contralateral to the affected limb and another electrode (anode) will be placed over the skull site that has been determined by TMS to produce a maximal motor contraction in the affected limb (33).

A 2mA current will be delivered using the surface rubber-carbon electrodes (35cm²) with surrounding saline soaked sponges (0.9% NaCl) by a battery driven, constant current stimulator (maximum output 10mA) (51). Participants will receive stimulation for 20 minutes while seated (prior to robotic motor training), with the anode over the optimal site for flexor carpi radialis (FCR) as identified using TMS, and the cathode on the contralateral supraorbital area (37). Sham tDCS: comparable set-up to real tDCS, 30 seconds real current ramping to 2mA at commencement, then after 5 seconds a slow decrease but to no current sustained for 20 minutes.

Robotic Training

We will use existing robots at the Feinstein Institute which are FDA-approved robotic devices that move the shoulder-and-elbow or wrist-and-forearm (used in a previous IRB protocol 11-121B). Following tDCS, the patient will be seated in a chair facing a video screen and the robot. The patient will hold onto the end of the robotic arm, and if this is not possible, then the patient's

affected arm will be placed in a foam-lined trough attached to the robot handle. Their hand and forearm will be held in place by Velcro® straps. The patient will move the robot arm as best he/she can through a series of exercises guided by a visual display on the video screen. The patient will see their moving arm and hand and see their movements recorded on the video screen. If a patient cannot move within 1.5 seconds, the device will move his/her arm through the exercises. These sessions will alternate the treatment of shoulder and elbow with wrist in successive sessions.

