Previous studies indicate that stroke patients may differentially respond to non-invasive motor cortex stimulation protocols according to whether the lesion includes cortex, or is confined to white matter (52). Accordingly, we will use blocked stratified randomization to ensure our two comparison groups are balanced with respect to this known prognostic factor (cortical versus subcortical classification). Classification of this grouping will be assessed using CT or MRI with 'subcortical' defined as a stroke without involvement of cortical motor areas, and 'cortical' as infarction of cortical primary or secondary sensorimotor areas in addition to subcortical infarction.

Randomization of patients is performed by a statistician and epidemiologist, [name]. She will communicate the status to [name]. The switch is covered so that the therapist and the PI will not know the group assignment.

Blinding

The study is double-blind. All investigators interacting with patients will be unaware which patients are receiving real or sham stimulation. This includes the principal investigator and research fellows conducting robotic, neurophysiology or clinical assessments. The tDCS device has a coding option to program sham or real stimulation. [name], a histopathologist in [name] lab who is not involved with the robot project and has agreed to perform this toggling task will set the tDCS device for any particular patient. She knows [name] and we will establish communication between [name] – who will determine the randomization and [name] so that [name] and the Research Associate to be named will not have the patient's code. It is important to note that once the machine to deliver the transcranial direct current stimulation is toggled no further manipulation of the device is needed. The tDCSM operates automatically to deliver current or not. We will receive the coding option from the collaborating institution, and will reveal this information after analysis, unless there is a need to inform the PI in case of an adverse event. Patients will be asked at visit 9 and visit 15 (mid-point and end of the intervention period), whether they think they received real or sham stimulation.

Statistical Considerations and Data Analysis

Specific Aim 1 (Clinical): Determine if there is a statistically significant difference in the change in upper limb Fugl-Meyer and Wolf Motor Function score between subjects trained with and without tDCS prior to robotic training.

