Methods to address specific aim 3: To assess the univariate relationship between treatment group and outcome, repeated measures ANOVA will be used in order to account for longitudinal evaluations. Multivariate methods will include linear mixed models and ANCOVA to adjust for interactions or other covariates potentially contributing to the association between treatment and outcome.

POWER: Based on the previous study by Lo et al., we can expect twelve weeks of upper limb robotic training to result in a 2.88 change in the FM score (5). We estimated that tDCS plus robotics would result in a FM change score of 4.33. Using a two-sided alpha and a standard deviation of approximately 1.5, enrolling 56 subjects (28 per group) would give us 90% power to detect a difference in Fugl-Myer score of 1.45 between the intervention groups. To account for potential subject attrition, we aim to increase our sample size by 15% thus resulting in an enrollment goal to 66 (33 subjects per group).

Specific Aim 4 (Clinical): Determine if there is a statistically significant difference in the change in verbal expression scores on the Apraxia Battery for Adults (ABA-2) and Philadelphia Naming Test Short Form (PNT short form) between subjects with aphasia trained with and without tDCS prior to robotic training.

Methods to address specific aim 4: We will compare demographic, clinical, and tDCS variables between intervention groups with aphasia using t-tests to compare means and chi-squared tests to compare proportions; where continuous data is non-parametric as defined by Shapiro-Wilk or Q-Q plots, we will use Kruskal Wallis tests. To assess the univariate relationship between treatment group and ABA-2 score, repeated measures ANOVA will be used in order to account for longitudinal evaluations. Multivariate methods will include linear mixed models and ANCOVA to adjust for interactions or other covariates potentially contributing to the association between treatment and outcome. Further, Pearson correlation coefficients will be assessed to identify any linear association between clinical and tDCS data points. The Spearman Rank correlation coefficient will be used for non-normally distributed variables. Fisher analyses will be used to look for differences in strength between groups.

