Specific Aim 5 (Biological): Examine whether blood levels of HMGB-1, and TNF,IL-1, IL-6, IL-8, IL-10, and BDNF change across rehabilitation intervention, and if those changes are correlated to functional recovery.

Methods to address specific aim 5. **The statistical analysis for this pilot study will be primarily descriptive in nature. The main statistical analysis will employ repeated measures analysis to describe the patterns of change in HMGB-1 and the cytokine values over time. Other techniques will be explored if the data warrant it; such as examining**

pairs of outcome variables (HMGB-1 and TNF, HMGB-1 and IL-1, or HMGB-1 and stroke severity; as pioneered at Feinstein by [name] and as in [57]).

Protection of Human Subjects

RISKS TO SUBJECTS

Human Subject Involvement and Characteristics: We anticipate enrolling 66 human subjects. Inclusion and exclusion criteria are stated above in the Research Design and Methods section. Subjects will be enrolled into one of two sites: the Feinstein Institute for Medical Research or the Burke Medical Research Institute.

Sources of Material: Sources of research material for participants from Feinstein will be the hospital records providing demographic and medical information including CT or MRI imaging studies, and clinical examinations performed at outpatient facilities run by the Department of Physical Medicine and Rehabilitation of the North Shore University Hospital (NSUH) and LIJ Medical Center (LIJMC). Sources of research material for study participants at Burke Medical Research Institute will be obtained through hospital records at the Burke Rehabilitation Hospital in White Plains, NY, and overseen by the Burke IRB.

Potential Risks:

TMS Risks: TMS is a technique that has been used widely and in a growing number of laboratories since 1985. A consensus was reached at the International Safety Conference on Transcranial Magnetic Stimulation, held at the National Institutes of Health in June of 1996, that single-pulse TMS and slow rTMS (with rates of stimulation less than one Hz) are safe. Subjects may experience mild headaches or neck pain, which are believed to be due to muscle tension and from the straight posture of the head and neck during the application of TMS. A rare possibility of activating a seizure in susceptible subjects has been documented.

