Blood Draw Risk: Minimal risks of blood withdrawal include pain from the needle being inserted through the skin into the vein, bruising, clot formation under the skin, lightheadedness, possible fainting and rarely infection.

Confidentiality Risk: One additional risk concerns the risk to confidentiality incurred with any collection of medical data.

ADEQUACY OF PROTECTION AGAINST RISKS

Recruitment and Informed Consent: Stroke subjects who meet inclusion criteria and do not meet exclusion criteria will be recruited at two sites by consenting professionals: the Burke Rehabilitation Hospital and the Department of Physical Medicine and Rehabilitation of NSUH and LIJMC.. Recruitment will be done with direct contact, flyers and letters sent to patients who have been enrolled on other research projects.

Recruitment of patients at Burke Rehabilitation Hospital will be primarily based on screening of the Burke outpatient list, as well as inpatient medical records for identifying future candidates, physician referral, advertising within the Burke network, on the Burke Website and collaborator websites. Participants enrolled at the Burke Medical Research Institute study site will be overseen by the Burke IRB, and its associated, approved study protocol and consent form.

Northwell Health physicians who have appropriate patient populations will be made aware of the research study protocol and procedures, and given an overview of the study through contacts with the study personnel. The physician will identify potential study participants. If the patient expresses interest in participation, the physician will either 1) obtain informed consent (if they are listed as an investigator on this study) or 2) provide the patient with the study coordinator's contact information or 3) provide the patient's contact information to study personnel with the patient's permission, which will be documented in the medical record.

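### Randomisation is stratified by lesion class but not by site, and site is not named in the Fugl-Meyer model, so a chance site imbalance is neither prevented nor adjusted for

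*Combined protocol and SAP*

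**What the plan says.** The Randomization section names a single stratification factor, cortical versus subcortical lesion: "we will use blocked stratified randomization to ensure our two comparison groups are balanced with respect to this known prognostic factor". It gives no block size, and it does not say whether the two sites share one list.

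The trial has two sites: "Subjects will be enrolled into one of two sites: the Feinstein Institute for Medical Research or the Burke Medical Research Institute". The Visit Schedule section states that "66 participants will be randomized to receive real or sham tDCS" and places visits in robot and TMS suites at one institute or the other. Under Clinical Outcome Measures, treatment generally follows recruitment; the example given is that "subjects recruited through Feinstein will be treated at Feinstein". Protection of Confidentiality refers to a robot suite at each institute.

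Recruitment and Informed Consent describes different sources. Burke relies mainly on screening its outpatient list, with inpatient records, referral and advertising; the other site works through its own health system's physicians. Burke participants are "overseen by the Burke IRB, and its associated, approved study protocol and consent form".

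For Aim 1, Statistical Considerations and Data Analysis plans a repeated-measures ANOVA of the Fugl-Meyer score, with mixed models and ANCOVA for covariates that it does not list. Neither site nor lesion class is named.

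**The concern.** Several features of the plan give reason to expect some difference between sites. The patients come from different sources, are trained in different suites, and at Burke are covered by a locally approved protocol that the reader cannot see. The Robotic Training section describes only one site's equipment: "We will use existing robots at the Feinstein Institute which are FDA-approved robotic devices".

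The target difference is 1.45 Fugl-Meyer points with a standard deviation of about 1.5. If the arms differ in their share of Burke patients, any site difference in Fugl-Meyer change enters the unadjusted treatment estimate in proportion to that gap. The plan has no step that prevents such a gap and no prespecified step that corrects for it. Adjustment could be added later, because site is known for every patient, but it would then be a modelling choice made after the data were seen.

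**Working it through.** **Inputs from the documents.** 66 randomised, 33 per arm; 56 evaluable before a 15% attrition allowance; target 4.33 − 2.88 = 1.45 points; SD about 1.5.

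**Assumed, because the documents do not give them.** Burke enrolment of 16, 22, 26 or 33 of 66; a site difference in Fugl-Meyer change of 0.5, 1.0 or 1.45 points; for the simulation, blocks of 4 and an even lesion mix.

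**1. The plan's own figure.** 56 / (1 − 0.15) = 65.9, so 66 is reproduced. (The alpha level is not stated. At two-sided 0.05, 90% power needs about 24 per group by t-test, so 28 is conservative. This does not affect the present point.)

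Standard error of the arm difference with 33 per group: 1.5 × √(2/33) = 0.37.

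**2. Chance imbalance when site is not a stratum.** Let B be the number at Burke and X the number of these on real tDCS. With 33:33 allocation X is hypergeometric (66, B, 33), and the gap in Burke share is |X − (B − X)| / 33 = |2X − B| / 33. For B = 26, Var(X) = 33 × (26/66) × (40/66) × (33/65) = 4.0, so SD(X) = 2.0 and the SD of the gap is 2 × 2.0 / 33 = 0.121.

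| Burke patients | SD of gap | Mean gap | P(gap ≥ 20 points) | P(gap ≥ 30 points) |
|---|---|---|---|---|
| 16 | 0.106 | 8.3 points | 4.2% | 0.8% |
| 22 | 0.117 | 9.1 points | 6.6% | 1.8% |
| 26 | 0.121 | 9.5 points | 7.7% | 2.3% |
| 33 | 0.124 | 10.0 points | 13.9% | 1.3% |

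Across these splits, the chance that all Burke patients fall in one arm is below 3 in 1,000,000.

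**3. Shift in the unadjusted estimate.** Shift = gap × site difference.

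- 0.20 × 0.5 = 0.10 points; 0.10 / 1.45 = 7% of target.
- 0.20 × 1.0 = 0.20 points; 14%.
- 0.20 × 1.45 = 0.29 points; 20%, or 0.29 / 0.37 = 0.8 of a standard error.

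At the mean gap the shift runs from 0.083 × 0.5 = 0.04 to 0.100 × 1.45 = 0.15 points (3 to 10%). Gaps move in steps of 2/33, so the smallest attainable value above 20 points is 21.2 (B = 33) or 24.2 (the other splits). At 24.2 points the range is 0.12 to 0.35.

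**4. Precision.** A site difference e adds variance q(1 − q)e², where q is the Burke share. With q = 26/66 this is 0.06, 0.24 or 0.50 for e = 0.5, 1.0 or 1.45. Against 1.5² = 2.25 that is 3%, 11% or 22% of the variance, which a site term could remove.

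**5. Average behaviour without site strata.** In 6,000 simulated trials per setting (33 Burke patients, blocks of 4 within lesion class, site differences of 0.5 to 1.5 points), mean bias was about zero and unadjusted type I error was 0.052 to 0.056 (Monte Carlo error about 0.003).

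**6. Effect of adding site as a stratum.** In the same kind of simulation with 16, 22 or 33 Burke patients, the root-mean-square gap fell from 0.11–0.12 to about 0.03, its 95th percentile from 0.20–0.24 to about 0.06, and the chance of a gap of 20 points or more from 4–11% to about zero. The required sample size does not change.

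**The case against.** The strongest reply is that randomisation already does its job. Allocation does not depend on site, the estimate is unbiased over randomisations, and type I error stays near nominal. Any unstratified covariate carries the same residual risk. This stands. A reader might infer that arm and site are confounded, or that one site could end up mostly real and the other mostly sham; the distribution above does not support either. It does not dispose of the point, because unbiasedness on average does not protect the one trial that is run.

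The scoring route is also largely closed. The outcome is change in Fugl-Meyer, assessors are blinded, and "Individual patient assessments will always be performed by the same evaluator to ensure internal consistency". A constant scoring offset between sites therefore cancels; only a site difference that changes between baseline and follow-up would remain. No further evaluator rule is needed.

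A reader might also assume that each site has its own therapists. The documents say only that a therapist administers and supervises procedures. Nor does a Burke-approved protocol show that training differs: it shows local oversight, and the robot algorithm is fixed.

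Large site effects are hard to square with the plan's own figures. A 3-point difference would exceed the expected robot-only change of 2.88, and with a 26/40 split would add variance 0.239 × 9 = 2.15, about 95% of the 2.25 implied by the planned SD. It is not used here.

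Finally, the analysis section leaves room for covariates, so one could say that site is already covered. It permits adjustment but does not commit to it.

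**Conclusion.** The point holds as a design improvement of modest size. Site is neither a named stratum nor a named model term in a two-site trial of 66 patients with a 1.45-point target. The consequence is a possible chance imbalance and some lost precision, without systematic bias. A typical imbalance would matter little. The unlucky case, a gap of 20 points or more with a 4 to 14% chance, would move the unadjusted estimate by about 0.10 to 0.29 points at a 20-point gap.

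These sizes rest on an assumed Burke enrolment of 16 to 33 patients and an assumed site difference of 0.5 to 1.45 points; the documents give neither. If the statistician already keeps a separate list for each site, the randomisation half is met in practice and only needs to be stated. The model term would still be missing.

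**What to change.** In the Randomization section, stratify the blocked randomisation by site as well as lesion class. That makes four cells averaging 66 / 4 = 16.5 patients, with small permuted blocks of varying size. In the Aim 1 analysis, name site and lesion class as fixed factors in the primary Fugl-Meyer model.

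If enrolment has begun, add both model terms now, before unblinding, and apply the site strata to the remaining patients.

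The cost is a new list from the same statistician, two sentences of text, one degree of freedom for each added factor, and a few incomplete blocks at the end of enrolment. The sample size is unaffected.

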Inclusion/Exclusion Criteria

Inclusion Criteria:

1. ≥ 18 years of age
2. First single focal unilateral lesion with diagnosis verified by brain imaging (MRI or CT scans) that occurred at least 6 months prior;
3. Cognitive function sufficient to understand the experiments and follow instructions (Mini-Mental Status Score of 24 or higher or interview for aphasic subjects);
4. Fugl-Meyer assessment 7 to 58 out of 66 (neither hemiplegic nor fully recovered motor function in the muscles of the shoulder and elbow and wrist).

Exclusion Criteria:

1. Botox treatment within 6-weeks of enrollment;
2. Fixed contraction deformity in the affected limb;
3. Complete and total flaccid paralysis of all shoulder and elbow motor performance;
4. History of hemorrhagic stroke
5. Ongoing use of CNS-active medications
6. Ongoing use of psychoactive medications, such as stimulants, antidepressants, and anti-psychotic medications
7. Presence of additional potential tDCS / TMS risk factors:
 - Damaged skin at the site of stimulation (i.e., skin with ingrown hairs, acne, razor nicks, wounds that have not healed, recent scar tissue, broken skin, etc.)
 - Presence of an electrically, magnetically or mechanically activated implant (including cardiac pacemaker), an intracerebral vascular clip, or any other electrically sensitive support system

- Metal in any part of the body, including metal injury to the eye (jewelry must be removed during stimulation)
- A history of medication-resistant epilepsy in the family
- Past history of seizures or unexplained spells of loss of consciousness

Visit Schedule

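### The cortical and subcortical stratum definitions are not complements: an eligible purely cortical motor infarct meets neither, and on one reading some lesions meet both

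*Combined protocol and SAP*

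**What the plan says.** Three statements in the Randomization section bear on the stratum.

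- **Rationale.** Patients may respond differently to motor cortex stimulation "according to whether the lesion includes cortex, or is confined to white matter".
- **Use.** The protocol says "we will use blocked stratified randomization to ensure our two comparison groups are balanced with respect to this known prognostic factor". No other stratification factor is named.
- **Definitions.** Subcortical is "a stroke without involvement of cortical motor areas". Cortical is "infarction of cortical primary or secondary sensorimotor areas in addition to subcortical infarction". Either CT or MRI may be used to classify.

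Eligibility on lesion site (Inclusion/Exclusion Criteria, inclusion criterion 2) is "First single focal unilateral lesion with diagnosis verified by brain imaging (MRI or CT scans) that occurred at least 6 months prior". It does not require a subcortical component, and no exclusion criterion removes purely cortical lesions. The Visit Schedule says that "66 participants will be randomized to receive real or sham tDCS".

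The documents give no third stratum, no tie-break and no named adjudicator for lesions that do not fit. The analysis of the Fugl-Meyer score (Statistical Considerations and Data Analysis, methods for Aim 1) is a repeated measures ANOVA on treatment group. Mixed models and ANCOVA follow with unnamed covariates, and the stratum is not mentioned.

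**The concern.** Stratified blocked allocation needs each patient to fall in exactly one stratum, because the stratum selects the list from which the assignment is drawn. Two features of the definitions prevent this:

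- One speaks of motor areas and the other of sensorimotor areas.
- Only the cortical definition adds a requirement for subcortical infarction.

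At stake is the quality of the one factor on which the protocol sets out to balance the arms. If a lesion has no stratum, or two, whoever classifies it must make a choice that the protocol does not record. Similar lesions could then be labelled differently, and the label is less useful both for balance and as a covariate.

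**Working it through.** The plan gives no figure to reproduce here. The check treats the two definitions as logical rules.

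**Inputs.** Describe a lesion by four yes/no features: M (cortical motor area), S (somatosensory part of sensorimotor cortex), O (other cortex) and W (subcortical infarct). At least one is present, so there are 2^4 − 1 = 15 patterns. Eligibility excludes none of them by site.

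**Rules as written.**

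- Subcortical: not M.
- Cortical, sensorimotor read broadly: (M or S) and W.
- Cortical, sensorimotor read as motor only: M and W.

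**Result.**

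| | Broad reading | Motor-only reading |
|---|---|---|
| Meets neither (M present, W absent) | 4 | 4 |
| Meets both (S and W present, M absent) | 2 | 0 |
| Meets exactly one | 9 | 11 |
| Total | 15 | 15 |

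The gap does not depend on the reading. With M present the lesion is not subcortical; with W absent it is not cortical. S and O can each be present or absent, which gives 2 × 2 = 4 patterns. The overlap does depend on the reading: it has 2 patterns (O present or absent) if somatosensory cortex counts as sensorimotor, and none otherwise. These are counts of logical patterns, not of patients.

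**Comparison with the rationale.** The rationale draws a third line, between any cortex and white matter only. A lesion with O but neither M nor S has one definite stratum under the written rule, subcortical, although it includes cortex. This is a difference between rationale and rule, not a gap or an overlap.

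**Possible number of patients.** The documents give no share of lesions without a unique stratum, so the shares below are assumptions applied to 66 patients:

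- 2%: 0.02 × 66 = 1.32, about 1 patient
- 5%: 0.05 × 66 = 3.3, about 3 patients
- 10%: 0.10 × 66 = 6.6, about 7 patients

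**Rule proposed below.** Cortical = M or S; subcortical = neither. Of the 16 combinations, 4 have M and S both absent, and one of those is empty. That leaves 3 subcortical patterns and 12 cortical, 3 + 12 = 15, with none in neither or both.

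**The case against.** The strongest reply is that this is loose drafting with an evident resolution. A purely cortical motor infarct fails the subcortical definition, the rationale sentence puts it on the cortex side, and there are only two strata, so a sensible reader calls it cortical. On the same view, motor and sensorimotor are shorthand for one region and the overlap disappears.

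Much of this stands. A reader might infer that such patients cannot be randomised; they can, by the placement just described. What remains is that this placement is not the written rule. Nor can the rationale sentence serve as a general tie-break, because it disagrees with the written rule on lesions of non-motor cortex. The overlap should be treated as conditional: the text uses two terms and does not say that they mean the same.

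Other inferences also go too far:

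- *That the two sites will classify the same lesion differently.* The documents do not say who reads the images or whether each site classifies its own patients. Inconsistency is possible, not shown.
- *That a planned subgroup analysis is compromised.* No cortical-versus-subcortical comparison is specified.
- *That lesions of other cortex are wrongly placed.* Taking motor-area involvement as the cut is a legitimate choice in a trial that stimulates motor cortex. The fault is only that rationale and rule do not match.

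**Conclusion.** The definitions are not complementary. The gap for purely cortical motor infarcts is certain on any reading; the overlap exists only if sensorimotor is broader than motor. The number of patients affected is unknown. The range of about 1 to 7 of 66 rests entirely on an assumed share of 2% to 10%, and nothing in the documents supports a particular value.

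A reader might infer that the treatment effect would be biased. It would not be in the unadjusted comparison of arms, provided that the stratum is assigned before allocation, since blocking then works within whatever label was given. The cost is limited to possible inconsistent classification and some loss of balance and precision on the only stated stratification factor. No sample size or power figure changes.

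**What to change.** Replace the two definitions with one rule in one anatomical term, applied to the imaging already required for eligibility and recorded before randomisation:

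- **Cortical:** any infarction of primary or secondary sensorimotor cortex, with or without subcortical infarction.
- **Subcortical:** every other eligible lesion.

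State that the cut is sensorimotor-cortex involvement rather than any cortex, and reword the rationale sentence to agree. Lesions confined to other cortex stay in the subcortical stratum under this rule; the rewording makes that a declared choice. Purely somatosensory cortical lesions become cortical, so the text should say that sensorimotor includes them.

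In the methods for Aim 1, name this stratum as a factor in the primary Fugl-Meyer model, so that the analysis reflects the way patients were allocated.

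The cost is a few sentences in the Randomization section and one term in the model. No extra imaging, visits or patients are needed.
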